8.3. Communication Between Investigational Sites

Investigational sites will be required to report AEs for all grades and attributions, SAEs, problems with study treatment administration, deviations, or any other problem that could affect the validity/integrity of the study data to the Sponsor-Investigator. All investigational sites will report AEs, ECIs and SAEs using the eCRFs and SAE reporting form. AEs will be reported within 5 business days of the investigator learning of the event. SAEs and ECIs will be reported within 1 business day of the investigator learning of the event. Problems with study treatment administration or any other problem affecting safety or data integrity should be communicated to the Sponsor-Investigator or designee per standard procedures by email or phone as soon as possible but within 2 business days of the Investigator learning of the event.

9. LABELING, PACKAGING, STORAGE AND RETURN OF CLINICAL SUPPLIES

9.1. Investigational Product

The Sponsor-Investigator shall be accountable for maintaining appropriate records and ensuring appropriate supply, storage, handling, distribution and usage of investigational product in accordance with the protocol and any applicable laws and regulations.

Clinical supplies will be provided by Merck as summarized in Table 6.

Table 6. Product Descriptions

Product Name & Potency	Dosage Form
Pembrolizumab 100 mg/ 4mL	Solution for Injection

9.2. Doxorubicin

Doxorubicin is commercially provided.

9.3. Packaging and Labeling Information

Clinical supplies will be affixed with a clinical label in accordance with regulatory requirements.

9.4. Storage and Handling Requirements

Clinical supplies must be stored in a secure, limited-access location under the storage conditions specified on the label.

Receipt and dispensing of trial medication must be recorded by an authorized person at the trial site.

Clinical supplies may not be used for any purpose other than that stated in the protocol.

9.5. Returns and Reconciliation

The Sponsor-Investigator is accountable for keeping accurate records of the clinical supplies received from Merck or designee and the amount dispensed to the subjects.

Upon completion or termination of the study, all unused investigational product will be destroyed at the site per institutional policy. It is the Sponsor-Investigator's or designee's responsibility to ensure arrangements are made for disposal of all empty or partially used containers, provided that procedures for proper disposal have been established according to applicable federal, state, local and institutional guidelines and procedures, and provided that appropriate records of disposal are kept.

9.6. Drug Accountability

All study drug will be stored at the investigational site in accordance with Good Clinical Practice (GCP) and Good Manufacturing Practices (GMP) requirements and will be inaccessible to unauthorized personnel.

An adequate record of receipt, distribution, and destruction of pembrolizumab will be kept in the form of a Drug Accountability Form and maintained by the LCI IDS (Investigational Drug Services) Pharmacy. The Investigator, or responsible party

designated by the Investigator, will maintain a careful record of the inventory using the Drug Accountability Form. Doxorubicin will be administered commercially.

9.7. Destruction

At the end of the study, unused supplies of pembrolizumab will be destroyed according to LCI IDS pharmacy policies.

10. SAFETY DATA COLLECTION, RECORDING AND REPORTING

Safety assessments will consist of monitoring and recording all adverse events and serious adverse events, regular monitoring of hematology, blood chemistry and liver function test values, regular measurement of vital signs, and performance of history and physical examinations. These assessments should be performed per the study calendar. Adverse events will be evaluated continuously throughout the study. Safety and tolerability, relationship to treatment and intensity will be assessed according to the Common Terminology Criteria for Adverse Events (CTCAE) version 4.0. All adverse events (Grades 1 – 5) will be documented in subject study charts, and recorded in the eCRF.

10.1. Unanticipated Problem Definition

An UAP is any incidence, experience or outcome that is unexpected, given the information provided in research-related documentation (e.g., Investigator's brochure, informed consent) and the study population characteristics that is related or possibly related to participation in the research study and places the participant at an increased risk.

10.2. Adverse Event

10.2.1. Adverse Event Definition

An adverse event is defined as any untoward medical occurrence in a study subject who is administered a pharmaceutical product and which does not necessarily have to have a causal relationship with this treatment. An adverse event can therefore be any unfavorable and unintended sign (including an abnormal laboratory finding, for example), symptom, or disease temporally associated with the use of a medicinal product or protocol-specified procedure, whether or not considered related to the medicinal product or protocol-specified procedure. Any worsening (i.e., any clinically significant adverse change in frequency and/or intensity) of a preexisting condition is also an adverse event.

Changes resulting from normal growth and development that do not vary significantly in frequency or severity from expected levels are not to be considered adverse events.

Examples of this may include, but are not limited to, typical crying in children and onset of menses or menopause occurring at a physiologically appropriate time in minor subjects.

Progression of the cancer under study is not considered an adverse event.

10.3. Evaluation of Adverse Events

A qualified investigator will evaluate all adverse events according to the NCI Common Terminology for Adverse Events (CTCAE), version 4.0.

Reporting period: AEs will be captured from the time of treatment initiation/re-initiation through 30 days following cessation of study treatment.

Exception:

- Adverse events that meet the definition of an Event of Clinical Interest (ECI) as defined in Section 10.11 will be reportable from informed consent if the ECI causes the subject to be excluded from the trial, or is the result of a protocol-specified intervention including but not limited to washout or discontinuation of usual therapy, diet, placebo treatment or a procedure.

Please refer to Section 10.11 for the definition and expedited reporting requirements for ECI's.

Adverse events will be evaluated for relatedness to both doxorubicin and pembrolizumab.

All adverse events regardless of CTCAE grade must also be evaluated for seriousness. Adverse events will be evaluated according to Table 7.

Table 7. Adverse Event Evaluation

V4.0 CTCAE Grading	Grade 1	Mild; asymptomatic or mild symptoms; clinical or diagnostic observations only; intervention not indicated.
	Grade 2	Moderate; minimal, local or noninvasive intervention indicated; limiting age-appropriate instrumental ADL.
	Grade 3	Severe or medically significant but not immediately life-threatening; hospitalization or prolongation of hospitalization indicated; disabling; limiting self-care ADL.
	Grade 4	Life threatening consequences; urgent intervention indicated.
	Grade 5	Death related to AE
Seriousness	A serious adverse event is any adverse event occurring at any dose or during any use of study treatment that:	
	†Results in death; or	
	†Is life threatening; or places the subject, in the view of the investigator, at immediate risk of death from the event as it occurred (Note: This does not include an adverse event that, had it occurred in a more severe form, might have caused death.); or	
	†Results in a persistent or significant disability/incapacity (substantial disruption of one’s ability to conduct normal life functions); or	
	†Results in or prolongs an existing inpatient hospitalization (hospitalization is defined as an inpatient admission, regardless of length of stay, even if the hospitalization is a precautionary measure for continued observation. (Note: Hospitalization for an elective procedure to treat a pre-existing condition that has not worsened is not a serious adverse event. A pre-existing condition is a clinical condition that is diagnosed prior to the use of a Merck product and is documented in the patient’s medical history.); or	
	†Is a congenital anomaly/birth defect (in offspring of subject taking the product regardless of time to diagnosis);or	
	Is a new cancer (that is not a condition of the study) (although not serious per ICH definition, is reportable to the Sponsor-Investigator within 24 hours and to Merck within 2 working days to meet certain local requirements); or	
	Is an overdose (whether accidental or intentional). Any adverse event associated with an overdose of pembrolizumab is considered a serious adverse event for collection purposes. An overdose that is not associated with an adverse event is considered a non-serious event of clinical interest and must be reported within 24 hours to the Sponsor-Investigator and to Merck within 2 working days.	
	Other important medical events that may not result in death, not be life threatening, or not require hospitalization may be considered a serious adverse event when, based upon appropriate medical judgment, the event may jeopardize the subject and may require medical or surgical intervention to prevent one of the outcomes listed previously (designated above by a †).	

Duration	Record the start and stop dates of the adverse event.	
Action taken	Did the adverse event cause pembrolizumab and/or doxorubicin to be discontinued?	
Relationship to study treatment	
Did pembrolizumab and/or doxorubicin cause the adverse event? The determination of the likelihood that pembrolizumab and/or doxorubicin caused the adverse event will be provided by an investigator who is a qualified physician. The investigator's signed/dated initials on the source document or worksheet that supports the causality noted on the AE form, ensures that a medically qualified assessment of causality was done. This initialed document must be retained for the required regulatory time frame. The criteria below are intended as reference guidelines to assist the investigator in assessing the likelihood of a relationship between pembrolizumab and/or doxorubicin and the adverse event based upon the available information.
 
The following components are to be used to assess the relationship between pembrolizumab and/or doxorubicin and the AE; the greater the correlation with the components and their respective elements (in number and/or intensity), the more likely pembrolizumab and/or doxorubicin caused the adverse event (AE):
	
	Exposure	Is there evidence that the subject was actually exposed to pembrolizumab and/or doxorubicin such as: reliable history, acceptable compliance assessment (expected pharmacologic effect, or measurement of drug/metabolite in bodily specimen)?
	Time Course	
Did the AE follow in a reasonable temporal sequence from administration of pembrolizumab and/or doxorubicin?
 
Is the time of onset of the AE compatible with a drug-induced effect (applies to trials with investigational medicinal product)?

	Likely Cause	Is the AE not reasonably explained by another etiology such as underlying disease, other drug(s)/vaccine(s), or other host or environmental factors

10.3.1. Relationship to Study Drug

The relationship to study drug therapy should be assessed using the following definitions:

Not Related: Evidence exists that the AE has an etiology other than the study drug (i.e., pre-existing condition, underlying disease, intercurrent illness, or concomitant medication). This includes events that are considered remotely or unlikely related to study drug.

Related: A temporal relationship exists between the event onset and administration of the study drug. It cannot be readily explained by the subject's clinical state, intercurrent illness, or concomitant therapies. In the case of cessation or reduction of the dose, the event abates or resolves and reappears upon rechallenge. It should be emphasized that ineffective study drug treatment should not be considered as causally related in the context of AE reporting. This includes events that are considered possibly, probably, or definitely related to study drug.

All adverse events (including event name, grade, start/stop date and attribution) will be documented in the medical record and/or research chart and recorded on the case report form for this protocol.

The Investigator is responsible for verifying and providing source documentation for all adverse events and assigning the attribution for each event for all subjects enrolled on the trial.

10.4. Suspected Adverse Reaction Definition

A SAR is an adverse event in which there is reasonable possibility that the study drug caused the adverse event as defined by 21 CFR 312.32. The Investigator is responsible for judging whether it is a reasonable possibility that the study drug caused the adverse event.

10.5. “Unexpected” Definition

An AE or SAR is to be considered unexpected if the event is not listed in the current Investigator Brochure, package insert or label or is not listed in the severity or specificity observed.

10.6. Serious Adverse Event Definition

An AE or SAR is to be considered serious if the Investigator deems it as such and the event results in any of the following outcomes:

- Death;
- Life-threatening situation (patient is at immediate risk of death);
- Inpatient hospitalization or prolongation of an existing hospitalization (excluding those for study drug administration, protocol-related procedures,

palliative or hospice care, or placement of an indwelling catheter, unless associated with other serious events);

- Persistent or significant disability/incapacity;
- Congenital anomaly/birth defect in the offspring of a subject who received study treatment;
- Development of a new cancer (that is not a condition of the study)
- Overdose of pembrolizumab as defined in Section 6.9, that is associated with an adverse event even if no other seriousness criteria are met;
- Other: Important medical events that may not result in death, be immediately life-threatening, or require hospitalization, may be considered an SAE when, based upon appropriate medical judgment, they may jeopardize the subject or may require medical or surgical intervention to prevent one of the outcomes listed in this definition.
 - **Examples of such events are:**
 - Intensive treatment in an emergency room or at home for allergic bronchospasm;
 - Blood dyscrasias or convulsions that do not result in hospitalization;
 - Development of drug dependency or drug abuse.
 - An AE or SAR is to be considered life-threatening if the Investigator deems it as such and the event poses an immediate threat of death.

Pregnancy and Lactation

Although pregnancy and lactation are not considered adverse events, pregnancies and lactations must be reported from informed consent through 120 days after last dose of pembrolizumab, or 30 days if the subject initiates new anti-cancer therapy, whichever is earliest. All reported pregnancies must be followed to the completion/termination of the pregnancy. Pregnancy outcomes of spontaneous abortion, missed abortion, benign hydatidiform mole, blighted ovum, fetal death, intrauterine death, miscarriage and stillbirth must be reported as SAEs. If the pregnancy continues to term, the outcome (health of infant) must also be reported.

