Serum creatinine OR measured or calculated creatinine clearance (CrCl) ^a (GFR can also be used in place of creatinine or CrCl)	≤ 1.5 X upper limit of normal (ULN) OR ≥ 60 mL/min for subjects with creatinine levels > 1.5 X institutional ULN
Hepatic	
Serum total bilirubin	≤ 1.5 X ULN OR Direct bilirubin \leq ULN for subjects with total bilirubin levels > 1.5 ULN
AST (SGOT) and ALT (SGPT)	≤ 2.5 X ULN OR ≤ 5 X ULN for subjects with liver metastases
Albumin	≥ 2.5 g/dL
Coagulation	

International Normalized Ratio (INR) or Prothrombin Time (PT)	≤ 1.5 X ULN unless the subject is receiving anticoagulant therapy as long as PT or PTT is within therapeutic range for intended use of coagulants
Activated Partial Thromboplastin Time (aPTT)	≤ 1.5 X ULN unless the subject is receiving anticoagulant therapy as long as PT or PTT is within therapeutic range for intended use of coagulants
^a Creatinine clearance should be calculated per institutional standard.	

- k. The subject has left ventricular ejection fraction (LVEF) $\geq 50\%$ assessed within 21 days prior to study treatment initiation.
- l. Subjects must not be expecting to conceive or father children within the timeframe referenced below. Subjects of childbearing potential must be willing to adhere to the contraception requirement as described in Section 3.3.2 from the day of the screening visit (or 14 days prior to the initiation of study treatment for oral contraception) throughout the study period up to 120 days after the last dose of pembrolizumab and/or up to 180 days after the last dose of doxorubicin. If there is any question that a subject of childbearing potential will not reliably comply with the requirements for contraception, that subject should not be entered into the study.
- m. Female subjects of childbearing potential must have a negative urine or serum pregnancy test at screening (within 72 hours of first dose of study treatment). If the urine test is positive or cannot be confirmed as negative, a serum pregnancy test will be required. The serum pregnancy test must be negative for the subject to be eligible.
- n. Subject has voluntarily agreed to participate by giving written informed consent for the trial. The subject may also provide consent for Optional and Future Studies-Biospecimen Collection. However, the subject may participate in the main trial without participating in Optional and Future Studies.

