3.3.2. Contraception/Reproduction

Pembrolizumab may have adverse effects on a fetus in utero. Furthermore, it is not known if pembrolizumab has transient adverse effects on the composition of sperm. For this trial, male subjects will be considered to be of non-reproductive potential if they have azoospermia (whether due to having had a vasectomy or due to an underlying medical condition).

Female subjects will be considered of non-reproductive potential if they are either:

(1) postmenopausal (defined as at least 12 months with no menses without an alternative medical cause; in women < 45 years of age a high follicle stimulating hormone (FSH) level in the postmenopausal range will be used to confirm a post-menopausal state in women not using hormonal contraception or hormonal replacement therapy).

OR

(2) have had a hysterectomy and/or bilateral oophorectomy, bilateral salpingectomy or bilateral tubal ligation/occlusion, at least 6 weeks prior to screening; documented hysterectomy or oophorectomy must be confirmed with medical records of the actual procedure or confirmed by an ultrasound. Tubal ligation must be confirmed with medical records of the actual procedure otherwise the subject must be willing to use two adequate barrier methods throughout the study, starting with the screening visit through 120 days after the last dose of pembrolizumab and up to 180 days after last dose of doxorubicin as specified in the protocol.

OR

(3) has a congenital or acquired condition that prevents childbearing.

Female and male subjects of reproductive potential must agree to avoid becoming pregnant or impregnating a partner, respectively, throughout the trial starting at the screening visit through 120 days after the last dose of pembrolizumab and/or for 180 days after receiving the last dose of doxorubicin by complying with one of the following:

(1) practice abstinence[†] from heterosexual activity;
OR

(2) use (or have their partner use) acceptable contraception during heterosexual activity.

Acceptable methods of contraception are[‡]:

Single method (one of the following is acceptable):

- intrauterine device (IUD)
- vasectomy of male subject or of a female subject's male partner
- contraceptive rod implanted into the skin

Combination method (requires use of two of the following):

- diaphragm with spermicide (cannot be used in conjunction with cervical cap/spermicide)
- cervical cap with spermicide (nulliparous women only)

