3.4. Use in Pregnancy

If a subject inadvertently becomes pregnant while on treatment with pembrolizumab, the subject will immediately be removed from the study treatment. The site will contact the subject at least monthly and document the subject's status until the pregnancy has been completed or terminated. The outcome of the pregnancy will be reported to the Sponsor-Investigator and to Merck without delay and within 24 hours to the Sponsor-Investigator and within 2 working days to Merck if the outcome is a serious adverse experience (e.g., death, abortion, congenital anomaly, or other disabling or life-threatening complication to the mother or newborn).

The study investigator will make every effort to obtain permission to follow the outcome of the pregnancy and report the condition of the fetus or newborn to the Sponsor-Investigator. If a male subject impregnates his female partner the study personnel at the site must be informed immediately and the pregnancy reported to the Sponsor-Investigator and to Merck and followed as described above and in Section 10.

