10.8. Expedited Safety Reporting to the Sponsor-Investigator

SAEs, ECIs, pregnancies and lactation exposure must be reported to the Sponsor-Investigator within 1 business day of awareness.

Reporting Period: SAEs and ECIs will be captured from the time of study treatment initiation/re-initiation through 90 days after the date of the last study treatment administration or 30 days if new anti-cancer therapy is initiated.

Exceptions:

- Reportable from informed consent:
 - Events that meet the definition of a SAE that are determined to be related and unexpected to a research procedure
 - Pregnancy and lactation; reportable through 120 days after last dose of pembrolizumab or 30 days if the subject initiates new anti-cancer therapy, whichever is earliest.
 - Events that meet the definition of an ECI (as defined per Section 10.7) if it causes the subject to be excluded from the trial, or is the result of a protocol-specified intervention, including but not limited to washout or discontinuation of usual therapy, diet, placebo treatment or a procedure (reportable until study treatment initiation).
- Reportable from study treatment initiation through duration of the subject's participation on the trial (treatment and follow-up):
 - Events occurring after the 30-day reporting period that are determined to be related to study treatment or a research procedure

SAEs will be followed until clinical recovery is complete and laboratory tests have returned to baseline, until progression has been stabilized, or until there has been acceptable resolution of the event. This may at times cause the follow-up period for SAEs to be greater than 90 days. Similarly, the Sponsor-Investigator is responsible for

following the subject during the required follow-up period even if the subject lives elsewhere or has been released from his or her care and is being treated under another service at LCI.

Please refer to Section 10.11 for the definition and expedited reporting requirements for ECI's.

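### Pregnancy reporting is tied to the last pembrolizumab dose only, so the end of the doxorubicin contraception period has no express reporting duty for female subjects: 60 days if both drugs stop together and no new therapy starts

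*Combined protocol and SAP*

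**What the plan says.** **Contraception.** Inclusion criterion l (Section 3.2.1) requires subjects of childbearing potential to use contraception "up to 120 days after the last dose of pembrolizumab and/or up to 180 days after the last dose of doxorubicin". Section 3.3.2 sets the same limits, "through 120 days after the last dose of pembrolizumab and/or for 180 days after receiving the last dose of doxorubicin". Each drug has its own clock.

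**Pregnancy reporting.** Section 10.6 requires reports from consent "through 120 days after last dose of pembrolizumab, or 30 days if the subject initiates new anti-cancer therapy, whichever is earliest". Section 10.8, on expedited reports to the Sponsor-Investigator, repeats the limit: "Pregnancy and lactation; reportable through 120 days after last dose of pembrolizumab or 30 days", the latter applying when new therapy starts. Section 10.11 uses it again for reports to the pembrolizumab manufacturer. None of the three names doxorubicin.

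**Other clauses that bear on the question.**
- The female-subject sentence of Section 3.4 opens "If a subject inadvertently becomes pregnant while on treatment with pembrolizumab". Its partner-pregnancy sentence has no such limit and no end date of its own, though it points to Section 10.
- Section 10.8 collects SAEs "through 90 days after the date of the last study treatment administration", or for 30 days if new therapy starts.
- Section 10.8 also has a late clause, running for as long as the subject takes part: "Events occurring after the 30-day reporting period that are determined to be related to study treatment or a research procedure".
- Section 10.6 states that pregnancy is not itself an adverse event, and lists pregnancy losses as outcomes to be reported as SAEs.

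**The concern.** The protocol treats the 180 days after doxorubicin as a period in which conception must be avoided. A contraception failure in that period is therefore something the trial should expect to hear about. The reporting clauses follow only the pembrolizumab clock, which can run out first.

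The consequence goes beyond a missing form. Section 10.6 says "All reported pregnancies must be followed to the completion/termination of the pregnancy". Follow-up to outcome is thus triggered by the report. Where nothing obliges the site to report, nothing expressly starts the follow-up, and the outcome of a pregnancy conceived within the protocol's own doxorubicin precaution period may go unrecorded.

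The case is foreseeable. Under Section 6.1, toxicity that requires pembrolizumab to be discontinued also ends doxorubicin on study. Under Section 6.11, documented progression ends treatment, so a subject who progresses while receiving both drugs can stop both together.

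**Working it through.** The plan gives no figure of its own for this point. The check is date arithmetic, followed by a search for a clause that closes the gap.

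**Inputs**
- Contraception after doxorubicin: 180 days (3.2.1 criterion l; 3.3.2).
- Pregnancy reporting after pembrolizumab: 120 days (10.6, 10.8).
- SAE collection after the last study treatment: 90 days (10.8).
- Cycle length: 21 days (6.1).

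**Assumptions.** No new anti-cancer therapy, and dosing on an exact 21-day schedule. Section 6.1 allows 3 days either way. While the gap is above zero, each day that pembrolizumab outlasts doxorubicin takes one day off it.

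**Formula.** Let L be the number of days by which the last pembrolizumab dose follows the last doxorubicin dose. Counted from the last doxorubicin dose, contraception ends on day 180 and reporting ends on day 120 + L. Then:

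gap = max(0, 180 − (120 + L)) = max(0, 60 − L)

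| Pembrolizumab outlasts doxorubicin by | L | Gap in days |
|---|---|---|
| 0 cycles | 0 | 60 − 0 = 60 |
| 1 cycle | 21 | 60 − 21 = 39 |
| 2 cycles | 42 | 60 − 42 = 18 |
| 3 cycles | 63 | 60 − 63 < 0, so 0 |

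**Doxorubicin given last.** L is then negative and the gap exceeds 60 days. For example, one doxorubicin dose 21 days after the final pembrolizumab dose gives 60 + 21 = 81. Section 6.11 expressly lets a subject leave study treatment and continue doxorubicin. Sections 6.1 and 6.5 also allow doxorubicin while pembrolizumab is withheld, and pembrolizumab might then never resume. The documents do not say how often either would happen.

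**New anti-cancer therapy.** Section 10.6 does not say from when the 30 days are counted. If they run from the last pembrolizumab dose and both drugs stopped together, 180 − 30 = 150 days of the contraception period carry no reporting duty.

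**Does another clause close the gap in the four cases tabulated?**
- *SAE window.* The last study treatment is the last pembrolizumab dose, so the window closes 90 days after it. Any gap opens after day 120, which is 120 − 90 = 30 days later. It covers 0 of the 60, 39 or 18 days.
- *Section 3.4, female subjects.* It applies only during pembrolizumab treatment and so has ended.
- *Section 3.4, partners.* It is not limited to treatment, but it concerns partners of male subjects only.
- *Late-event clause of 10.8.* It needs an event judged related. Pregnancy is expressly not an adverse event and is not named there, so an uncomplicated or unattributed pregnancy is not expressly caught.
- *Congenital anomaly.* Table 7 makes it serious whenever it is diagnosed. That captures one outcome, not the pregnancy.
- *Reporting within one business day of awareness (10.8).* This sets how fast a report is made. The same section sets the period.

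**The case against.** The best reply is that the outcomes that matter most already have routes. The sentence in 10.6 on pregnancy losses has no end date of its own. An anomaly in a treated subject's offspring is serious regardless of when it is found. The late-event clause runs through the subject's participation, and Section 10.3.1 counts even a possible relationship as related, so a loss or anomaly in the doxorubicin precaution period could readily qualify. This stands, and it narrows the point to uncomplicated or unattributed pregnancies in female subjects.

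It can also be said that nothing in the documents requires the two windows to match: contraception is a precaution, reporting is surveillance, and pembrolizumab is the drug supplied for the study. That explains the limit in 10.11. It is weaker for reports to the Sponsor-Investigator, because Section 10.3 has adverse events assessed against both drugs and the SAE window in 10.8 is tied to study treatment as a whole.

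A third reply is that aligning the windows while keeping the 30-day new-therapy cut-off leaves a larger shortfall than the one repaired. This is correct where new therapy starts, and the fix should say so openly.

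A reader might infer that toxicity ending both drugs is the usual way treatment stops, or that the gap closes at a fixed pembrolizumab cycle once the doxorubicin cap is reached. The documents support neither. They give no frequencies for stopping reasons. The number of doses under the 450 mg/m² cap depends on when the dose is raised: 60 + 5 × 75 = 435 is 6 doses, while 5 × 60 + 2 × 75 = 450 is 7.

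**Conclusion.** The point holds as a minor inconsistency in safety reporting. With no new anti-cancer therapy and exact 21-day cycles, the period with no express duty for female subjects is 60, 39, 18 or 0 days when pembrolizumab outlasts doxorubicin by 0, 1, 2 or at least 3 cycles. It is longer if doxorubicin is given last.

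Two wider readings should be resisted. The first is that every subject has a 60-day gap: anyone who continues pembrolizumab for at least 60 days after doxorubicin has none. The second is that the trial's conclusions are at risk. The contraception requirement itself is intact, a pregnancy does not count as an adverse event, and the stopping rule and efficacy analyses do not change.

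At most 30 subjects enrol, and the documents do not give the number of women of reproductive potential, so the expected number of missed pregnancies cannot be estimated.

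**What to change.** 1. In Sections 10.6 and 10.8, make pregnancies reportable to the Sponsor-Investigator from consent through the later of 120 days after the last pembrolizumab dose and 180 days after the last doxorubicin dose. Without new therapy, this brings the gap to 0 for every dosing sequence.
2. In Section 3.4, extend the female-subject sentence to treatment with pembrolizumab and/or doxorubicin, so that it also covers a subject receiving doxorubicin while pembrolizumab is held or stopped.
3. Section 10.11 may stay as it is.
4. Treat the 30-day new-therapy cut-off as a separate decision. If it is kept, state that it leaves up to 150 days of the contraception period without a reporting duty when both drugs stop together, and say from when the 30 days are counted.

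The cost is a phrase in each of three sections, one clarifying sentence on the cut-off, and a few extra reports at most among 30 subjects. Sample size, stopping rule and analyses are unchanged.
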